8 MEASUREMENT OF EFFECT

PET scans must be done at screening, within 14 days of Cycle 6 Day 1, and to confirm CR (if applicable). During the study period, all subjects will be evaluated for response by CT (if contrast CT is contraindicated MRI with a non-contrast CT Chest should be completed) within 14 days of Day 1 of Cycles 3, 6, and 12. After Cycle 12, subjects should be evaluated for response by CT (if contrast CT is contraindicated MRI with a non-contrast CT Chest should be completed) approximately every 6 cycles through cycle 24 unless clinically indicated sooner (at the discretion of the treating physician). Subjects achieving stable disease or better should continue daily treatment with umbralisib for a duration of 24 cycles (approximately 24 months). Response assessments for PFS after cycle 24 should occur at least every 12 months. All baseline assessments to characterize disease will be performed within 30 days of Cycle 1 Day 1, prior to initiation of therapy. During the treatment period, all efficacy assessments have a +/- 14 day window. The determination of response and progression will be based on the International Working Group (IWG) Revised Response Criteria for Malignant Lymphoma (Cheson et al., 2007, See Appendix D) modified so that the six index lesions include both nodal and extranodal lesions as described in the Lugano classification (Cheson et al. 2014) rather than considering nodal and extranodal lesions separately.

Subjects will remain on study treatment (for a duration of 24 months) until the occurrence of definitive disease progression, unacceptable toxicity, or withdrawal from the study due to investigator decision or other reasons. Subjects who discontinue from study treatment for any reason other than PD will continue to be followed for progression, as per the protocol.

8.1 METHOD OF ASSESSMENT

CT scan is the preferred method for radiographic tumor assessment. CT with iodinated IV contrast is preferred. If iodinated contrast is contraindicated, a non-contrast chest CT coupled with a gadolinium-enhanced MRI of the abdomen/pelvis (and neck as clinically warranted) is an acceptable substitute. Chest x-ray, ultrasound, endoscopy, laparoscopy, or tumor markers will not be considered for response assessment. PET using fluorodeoxyglucose (FDG) should be done at screening for all subjects, approximately 14 days of Day 1 of Cycle 6 and then to confirm a potential CR for subjects with FDG-avid disease.

Bone marrow assessment should be used to assess response to therapy if the subject was deemed to have disease in the bone marrow prior to initiation of protocol therapy and at the discretion of the investigator.

For radiographic evaluations, the same method of assessment and the same technique (e.g., scan type, subject position, dose of contrast, injection/scan interval) should be used to characterize each identified and reported lesion at baseline and during study treatment and follow-up. However, if a subject is imaged without contrast at baseline, subsequent assessments should be performed with contrast, unless medically contraindicated.

All baseline assessments to characterize disease will be performed within 30 days of Cycle 1 Day 1, prior to initiation of therapy.

8.2 RESPONSE REVIEW

The review of radiographic and clinical data by the study investigators will be performed on an ongoing basis. De-identified images should be available if the Sponsor requests to confirm any objective response observed.

8.3 ANTITUMOR EFFECT

Assessment of lymphoma response (CR, PR or SD) and disease progression will be evaluated as outlined in the schedule of events, according to the Revised Response Criteria for Malignant Lymphoma for NHL subjects (Cheson et al., 2007). Overall response rate, CR, PR, SD, PFS and DOR will be calculated as detailed below.

8.4 DEFINITIONS OF TUMOR RESPONSE AND PROGRESSION

Evaluable for objective response. Only those subjects who have had a pre-treatment baseline efficacy evaluation and at least one post-treatment efficacy evaluation will be considered evaluable for response. These subjects will have their response classified according to the definitions stated below.

8.4.1 COMPLETE RESPONSE

Complete response (CR) is defined as the complete disappearance of all evidence of disease and disease-related symptoms. The spleen and/or liver, if considered enlarged before therapy, on the basis of physical exam or CT scan, should not be palpable on physical examination and should be considered normal size by imaging studies, and nodules related to lymphoma should disappear. Bone marrow infiltrate cleared on repeat biopsy, if indeterminate by morphology, immunohistochemistry should be negative (Cheson et al., 2007).

In subjects with FDG-avid lymphoma with a positive PET scan before therapy or no pretreatment PET scan, a post-treatment residual mass of any size is permitted as long as it is PET negative. In subjects with variably FDG-avid lymphomas or where FDG-avidity is unknown, all lymph node and nodal masses must have regressed on CT to normal size (≤ 1.5 cm in their greatest transverse diameter for nodes > 1.5 cm before therapy). Previously involved nodes that were 1.1 to 1.5 cm in the long axis and more than 1.0 cm on their short axis before treatment must have decreased to ≤ 1.0 cm in their short axis after treatment (Cheson et al., 2007).

8.4.2 PARTIAL RESPONSE

Partial response (PR) is defined as the regression of measurable disease and no new sites of disease. Regression is defined as greater than or equal to 50% decrease in the sum of the products of the diameters (SPD) of the index lesions, coupled with no unequivocal increase in size of other lymph nodes, liver or spleen. No new sites of disease should be observed. In subjects with FDG-avid lymphoma with no pretreatment PET scan or if the PET scan was positive before therapy, the post-treatment PET should be positive in at least one previously involved site. For subjects with variably

UTX-TGR-203

Dated: 20 December 2018 (Ver 2.0)

Page 49 of 85

FDG-avid lymphomas or where FDG-avidity is unknown, if no pretreatment PET scan is available, or if a pretreatment PET scan was negative, CT criteria should be used. If bone marrow was involved prior to therapy and a clinical CR was achieved but no bone marrow assessment is completed after treatment then these subjects are considered partial responders (Cheson et al., 2007).

8.4.3 STABLE DISEASE

Stable disease is defined as the failure to attain CR/PR but does not fulfill the criteria for progressive disease. For subjects with FDG-avid lymphomas, the PET scan should be positive at prior sites of disease and there should be no new areas of involvement. For those with disease evaluated by CT only, there must be no unequivocal change in the size of the previous lesions on the post-treatment CT scan (Cheson et al., 2007).

8.4.4 PROGRESSION OF DISEASE

Any of the following conditions will constitute relapsed or progressive disease:

Appearance of any new lesion more than 1.5 cm in any axis, even if other lesions are decreasing in size will be considered relapsed or progressive disease. Increase in FDG uptake in a previously unaffected site should be confirmed with other modalities, a therapeutic decision should not be made solely on the basis of PET without histologic confirmation (Cheson et al., 2007).

There is at least a 50% increase from nadir in one of the following:

- The SPD of index lesions,
- The greatest transverse diameter (GTD) of any individual previously involved node, or
- The GTD of any previously involved node provided that the GTD of that node is now ≥ 1.5 cm.

Lesions should be PET positive if observed in a typical FDG-avid lymphoma or the lesion was PET positive before therapy unless the lesion is too small to be detected with current PET systems (< 1.5 cm in its long axis by CT) (Cheson et al., 2007).

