- A patient is considered to have SD when he or she fails to attain the criteria needed for a CR or PR, but does not fulfill those for progressive disease (see Relapsed Disease [after CR]/Progressive Disease [after PR, SD]).
- Typically FGD-avid lymphomas: the PET should be positive at prior sites of disease with no new areas of involvement on the post-treatment CT or PET.
- Variably FDG-avid lymphomas/FDG-avidity unknown: for patients without a pretreatment PET scan or if the pretreatment PET was negative, there must be no change in the size of the previous lesions on the post-treatment CT scan.

Relapsed Disease (after CR) / Progressive Disease (after PR, SD):

Lymph nodes should be considered abnormal if the long axis is more than 1.5 cm regardless of the short axis. If a lymph node has a long axis of 1.1 to 1.5 cm, it should only be considered abnormal if its short axis is more than 1.0. Lymph nodes $\leq 1.0 \times \leq 1.0$ cm will not be considered as abnormal for relapse or progressive disease.

- Appearance of any new lesion more than 1.5 cm in any axis during or at the end of therapy, even if other lesions are decreasing in size. Increased FDG uptake in a previously unaffected site should only be considered relapsed or progressive disease after confirmation with other modalities. In patients with no prior history of pulmonary lymphoma, new lung nodules identified by CT are mostly benign. Thus, a therapeutic decision should not be made solely on the basis of the PET without histologic confirmation.
- At least a 50% increase from nadir in the SPD of any previously involved nodes, or in a single involved node, or the size of other lesions (e.g., splenic or hepatic nodules). To be considered progressive disease, a lymph node with a diameter of the short axis of less than 1.0 cm must increase by $\geq 50\%$ and to a size of 1.5 x 1.5 cm or more than 1.5 cm in the long axis.
- At least a 50% increase in the longest diameter of any single previously identified node more than 1 cm in its short axis.
- Lesions should be PET positive if observed in a typical FDG-avid lymphoma or the lesion was PET positive before therapy unless the lesion is too small to be detected with current PET systems (< 1.5 cm in its long axis by CT).

Measurable extranodal disease should be assessed in a manner similar to that for nodal disease. For these recommendations, the spleen is considered nodal disease. Disease that is only assessable (e.g.,

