pleural effusions, bone lesions) will be recorded as present or absent only, unless, while an abnormality is still noted by imaging studies or physical examination, it is found to be histologically negative.

In clinical trials where PET is unavailable to the vast majority of participants, or where PET is not deemed necessary or appropriate for use (e.g., a trial in patients with MALT lymphoma), response should be assessed as above, but only using CT scans. However, residual masses should not be assigned CRu status, but should be considered partial responses.

Response Assessment:

Response Definitions for Clinical Trials

Response	Definition	Nodal Masses	Spleen, Liver	Bone Marrow
CR	Disappearance of all evidence of disease	
 FDG-avid or PET positive prior to therapy; mass of any size permitted if PET negative Variably FDG-avid or PET negative; regression to normal size on CT 	Not palpable, nodules disappeared	Infiltrate cleared on repeat biopsy; if indeterminate by morphology, immunohistochemistry should be negative
PR	Regression of measurable disease and no new sites	
 ≥50% decrease in SPD of up to 6 largest dominant masses; no increase in size of other nodes FDG-avid or PET positive prior to therapy; one or more PET positive at previously involved site Variably FDG-avid or PET negative; regression on CT 	≥50% decrease in SPD of nodules (for single nodule in greatest transverse diameter); no increase in size of liver or spleen	Irrelevant if positive prior to therapy; cell type should be specified

Response Definitions for Clinical Trials (continued)

Response	Definition	Nodal Masses	Spleen, Liver	Bone Marrow
SD	Failure to attain CR/PR or PD	
 FDG-avid or PET positive prior to therapy; PET positive at prior sites of disease and no new sites on CT or PET Variably FDG-avid or PET negative; no change in size of previous lesions on CT 	—	—
Relapsed disease or PD	Any new lesion or increase by $\geq 50\%$ of previously involved sites from nadir	
 Appearance of a new lesion(s) >1.5 cm in any axis, $\geq 50\%$ increase in SPD of more than one node, or $\geq 50\%$ increase in longest diameter of a previously identified node >1 cm in short axis Lesions PET positive if FDG-avid lymphoma or PET positive prior to therapy 	$>50\%$ increase from nadir in the SPD of any previous lesions	New or recurrent involvement

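### Section 8.4.4 counts 50% growth in any single node as progression, however small the node, which disables its own 1.5 cm floor and departs from Appendix D

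*Combined protocol and SAP*

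**What the plan says.** Section 8.4.4 needs only one of three growth conditions, each a rise of at least 50% from nadir. The first is the SPD of the index lesions. The second is "The greatest transverse diameter (GTD) of any individual previously involved node, or". The third is "The GTD of any previously involved node provided that the GTD of that node is now" 1.5 cm or more. The section then asks that lesions be PET positive where PET applies, "unless the lesion is too small to be detected with current PET systems", which it sets at under 1.5 cm in long axis by CT.

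Appendix D sets out the 2007 criteria and treats small nodes differently in three ways:
- A node no larger than 1.0 x 1.0 cm "will not be considered as abnormal for relapse or progressive disease".
- A node with short axis under 1.0 cm must grow by at least 50% "and to a size of 1.5 x 1.5 cm or more than 1.5 cm in the long axis".
- The longest-diameter rule asks for a 50% increase "in the longest diameter of any single previously identified node more than 1 cm in its short axis". The summary table at the end of Appendix D repeats this as an "increase in longest diameter of a previously identified node >1 cm in short axis".

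Section 2.2 defines definitive progression by the 2007 criteria. Section 8 bases progression on Appendix D and declares one modification: the six index lesions pool nodal and extranodal disease.

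**The concern.** The second and third bullets of Section 8.4.4 test the same quantity and differ only in the floor. Because either is enough, the version without the floor decides every case. The nodes affected are those that have shrunk below 1.0 cm, so the subjects exposed are mostly responders.

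A progression call is a PFS event and ends DOR (Section 2.2), and disease progression is a reason to stop study treatment (Section 4.5). Response is read by the investigators (Section 8.2) at up to 15 sites. One reader following Section 8.4.4 and another following Appendix D could code the same scans differently. The error would bring progression forward, so it runs against the regimen.

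**Working it through.** **Inputs.** The three bullets come from Section 8.4.4, the node-size rules from Appendix D, and the normal-size limit for CR by CT from Section 8.4.1. The plan gives no figure of its own to reproduce. GTD is taken to be the long axis on CT.

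**Step 1: does the floor ever act?** Let n be the nadir GTD and c the current GTD.
- Second bullet: c ≥ 1.5n.
- Third bullet: c ≥ 1.5n and c ≥ 1.5 cm.

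Every node that meets the third bullet meets the second. The floor could matter only where 1.5n < 1.5 cm, that is n < 1.0 cm, and there the second bullet has already called progression. A grid check (nadir long axis 3 to 30 mm, current long axis up to 60 mm, 1 mm steps) found 0 cases meeting the third bullet but not the second, and 956 the other way. The count of 956 depends on the grid chosen; the zero does not.

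**Step 2: where does the second bullet fire?** The threshold is 1.5n. The growth needed to reach 1.5 cm is 1.5/n − 1.

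| Nadir GTD (cm) | Second bullet fires at (cm) | Growth needed to reach 1.5 cm |
|---|---|---|
| 0.6 | 0.90 | 150% |
| 0.7 | 1.05 | 114% |
| 0.8 | 1.20 | 88% |
| 0.9 | 1.35 | 67% |
| 1.0 | 1.50 | 50% |

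**Step 3: compare with Appendix D.** Take a node over 1.5 cm before therapy that shrinks to 0.8 x 0.6 cm and later measures 1.2 x 0.9 cm.
- Section 8.4.4: 1.2/0.8 = 1.50, so progression.
- Appendix D: short axis is under 1.0 cm throughout and the node has reached neither 1.5 x 1.5 cm nor more than 1.5 cm in long axis, so not progression.
- Section 8.4.1: at 1.2 cm the node is still within the 1.5 cm normal-size limit used for CR by CT.

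**Step 4: does PET rescue the text?** No. Every node in the first four rows is under 1.5 cm when the second bullet fires, and lesions of that size are exempt from the PET condition.

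**Step 5: would keeping only the third bullet be enough?** Not quite. A node going from 0.9 x 0.7 to 1.5 x 1.1 cm meets the third bullet (1.5/0.9 = 1.67, and 1.5 cm reached). It fails Appendix D, because it is neither 1.5 x 1.5 cm nor more than 1.5 cm long.

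**Step 6: illustration of frequency, on assumptions only.** The documents give no measurement error. Assume stable 0.8 cm nodes, five on-treatment scans (Cycles 3, 6, 12, 18 and 24), short axis 0.8 times GTD, and independent normal errors on each axis with SD 0.5 / 1.0 / 1.5 mm. The simulation used 200,000 subjects per setting. The relevant figure is what the second bullet adds to the false progression that the SPD bullet already produces.
- One node: SPD bullet alone 1.9 / 42.9 / 70.8%; with the second bullet 1.9 / 43.3 / 72.2%. Added: 0.0 / 0.4 / 1.4 points.
- Three nodes: added about 0 / 12 / 33 points.
- Six nodes: SPD bullet alone 0.0 / 0.3 / 8.6%; Section 8.4.4 as written 0.0 / 26.5 / 81.5%. Added: 0 / 26 / 73 points.

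The SPD component is not charged to this defect, because Appendix D also has an SPD criterion; its table lists an "increase in SPD of more than one node" without a floor.

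**The case against.** **The governing criteria are named.** A reader might infer that the documents leave it open which rule governs. They do not leave it fully open: Sections 2.2, 8, 8.3 and 9.2 all name the 2007 criteria, and Section 8 points to Appendix D. The sentence in Section 9.2 that ends treatment refers to progression by the corresponding criteria, which there are the 2007 criteria, so it does not tie the stop to the second bullet. This part of the objection stands: the documents lean towards Appendix D. It does not remove the conflict. Section 8.4 tells readers to classify by the definitions beneath it, and Section 8.4.4 cites the 2007 criteria as its own source, so a site using it has no sign that it departs from them.

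**Appendix D is not uniformly strict.** A reader might infer that it bars single-node progression unless short axis exceeds 1 cm. Its SPD item also covers a single involved node, with a size floor only for short axis under 1.0 cm. The contradiction is therefore confined to nodes under that limit.

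**The reach is limited.** Non-index lesions need not be measured (Section 8.5), so mainly the index nodes, at most six, are exposed. PFS and DOR are secondary. Section 9 defers derivations to a formal SAP due before database lock, so coding could still be settled there. That is fair, but it would come after the sites' treatment decisions.

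**Conclusion.** The text is wrong as written. The second bullet makes the 1.5 cm floor inoperative, and for nodes with short axis under 1.0 cm it calls progression where Appendix D does not. This follows from the wording and the threshold arithmetic; it needs no assumption beyond reading GTD as the CT long axis.

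The direction is towards shorter PFS and DOR, and possibly earlier treatment stop, in responders. The primary endpoint is little affected, because best response is counted up to progression (Section 8.6).

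The size of the effect cannot be derived from the documents. A reader might take a large false-progression rate from the simulation, but the documents do not support one. On assumed error the addition is nil at 0.5 mm and negligible with one index node. It becomes large only with several small nodes, larger errors and independence between nodes. The grade is a should-fix at the low end.

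**What to change.** 1. Delete the second bullet of Section 8.4.4.
2. Replace the single-node rule there with Appendix D's wording, copied verbatim. That covers the size requirement for a short axis under 1.0 cm, the longest-diameter rule for nodes over 1 cm in short axis, and the statement on nodes within 1.0 x 1.0 cm.
3. State that Appendix D prevails over Section 8.4 except for the pooled index lesions.

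No further rule is needed. An SPD exemption for small nodes or a changed short-axis cut-off would go beyond Appendix D. The cost is protocol wording and a note to sites, with no new procedures or data.

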8.5 DEFINITIONS OF DISEASE PARAMETERS

Measurable disease: Measurable lesions are defined as those that can be accurately measured in at least two dimensions with conventional techniques (CT, PET/CT, MRI, x-ray) and meet one of the following criteria: nodal lesion with a long axis > 1.5 cm regardless of short axis, nodal lesion with long and short axes ≥ 1.0 cm, or extranodal lesions with long and short axes ≥ 1.0 cm with spiral CT scan. All tumor measurements should be recorded in centimeters.

Non-measurable disease (evaluable disease): All other lesions (or sites of disease) including small lesions, (< 1.0 cm using spiral CT scan) are considered non-measurable disease. Bone lesions, leptomeningeal disease, ascites, pleural/pericardial effusions, lymphangitis, and cystic lesions are all non-measurable.

Index lesions: All measurable lesions up to a maximum of 6 nodal and extranodal lesions total, representative of all involved organs, should be identified as **index lesions** and recorded and measured at baseline. Index lesions should be selected on the basis of their size (clearly measurable in two perpendicular dimensions), and the highest FDG avidity (high SUV lesions may be prioritized even if not the largest lesions, and their suitability for accurate repeated measurements (either by imaging techniques or clinically). A baseline sum of product of the diameters (SPD) for all index lesions will be calculated and reported as the baseline SPD. The baseline SPD will be used as reference to further characterize any objective tumor regression in the measurable dimension of the disease.

Non-index lesions: All other lesions (or sites of disease) including any measurable lesions over and above the 6 index lesions should be identified as **non-index lesions** and should also be recorded at baseline. Measurements of these lesions are not required, but the presence, absence, or in rare cases unequivocal progression of each should be noted throughout follow-up.

8.6 EVALUATION OF BEST OVERALL RESPONSE

The best overall response is the best response recorded from the start of the treatment until disease progression/recurrence (taking as reference for progressive disease the smallest measurements recorded since the treatment started). The subject's best response assignment will depend on the achievement of both measurement and confirmation criteria as per the NHL established criteria used in this study (See Appendix A).

8.6.1 DURATION OF RESPONSE

Duration of response is defined as the time from documentation of a response to treatment to the first documentation of tumor progression or death due to any cause whichever comes first. Duration of the response will be summarized using n (sample size), mean, standard deviation, median, minimum, and maximum for the responders.

Duration of stable disease:

Stable disease is measured from the start of the treatment until the criteria for progression are met.

[figure not shown]
Progression-Free Survival:

Progression free survival (PFS) is defined as the time from study entry to the first documentation of tumor progression or death due to any cause whichever comes first. This variable will be analyzed via Kaplan-Meier methodology. The median PFS will be estimated.

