2 OBJECTIVES AND ENDPOINTS

2.1 STUDY OBJECTIVES

PRIMARY OBJECTIVE

- To assess the overall response rate (ORR) in subjects with treatment naïve follicular lymphoma (FL) and small lymphocytic lymphoma (SLL) treated with umbralisib in combination with ublituximab.

KEY SECONDARY OBJECTIVES

- To evaluate the safety of umbralisib in combination with ublituximab.
- To assess the duration of response (DOR), Complete Response (CR) and progression-free survival (PFS) in subjects with treatment naïve follicular lymphoma and small lymphocytic lymphoma treated with umbralisib + ublituximab.

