4.4 STUDY SITES

Up to 15 trial centers in the United States may participate in this study. Enrollment is expected to be completed in approximately 12-16 months.

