9 STATISTICAL CONSIDERATIONS

The sections of the Statistical Considerations describe the statistical methods to be used to analyze the efficacy and safety. These methods may be revised and updated due to reasons such as regulatory requirements or need for further clarifications. The final analysis plan will be documented in a formal statistical analysis plan (SAP) that must be finalized before database lock. The SAP will include details on how variables will be derived, how missing data will be handled, and how censoring procedures will be applied to time to event related variables as well as the details on statistical methods to be used for safety and efficacy analyses. The final clinical study report will discuss deviations from the SAP, if any.

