9.1 SAMPLE SIZE AND POWER

9.2 GENERAL ANALYSIS CONVENTION

This is an open-label, Phase 2, study of the PI3K delta inhibitor umbralisib in combination with ublituximab. This trial is designed to evaluate the overall response rate (CR + PR), as well as duration of response (DOR), complete response (CR), and progression-free survival (PFS) in treatment naïve follicular lymphoma and small lymphocytic lymphoma subjects. Assessment of lymphoma response (CR, PR or SD) and disease progression will be evaluated as outlined in the schedule of assessments (Section 5), according to the Revised Response Criteria for Malignant Lymphoma (Cheson et al. 2007). Subjects who progress according to the corresponding criteria will receive no further treatment. Subjects who respond to the treatment (i.e., CR, PR or SD) may remain on trial.

Safety will be examined on an ongoing basis while the study is being conducted. Toxicity will be assessed utilizing the National Cancer Institute Common Terminology Criteria for Adverse Events (NCI CTCAE) v4.0 (<http://evs.nci.nih.gov/ftp1/CTCAE>).

Unless otherwise stated, all analyses will be performed using SAS Version 9.4 or higher and all hypothesis tests will be conducted at a two-sided significance level of 0.05.

In general, summary tabulations will display the number of observations, mean, standard deviation, median, minimum, maximum, and appropriate percentiles for continuous variables, and the number and percentage by category for categorical data. Summaries will be presented. The data listings will include all available efficacy and safety data.

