9.7 EFFICACY ANALYSES

Two populations will be used in the efficacy analyses, Intent-to-Treat (ITT) and Per Protocol (PP) populations. The ITT population will include all safety population who provide efficacy assessment, and PP population will include all ITT population without major protocol violations.

The efficacy endpoints will include:

- Overall response rate (ORR)
- Complete response (CR)
- Duration of Response (DoR)
- Progression-free Survival (PFS)

These variables will be analyzed/summarized based on the ITT population as well as the PP population as appropriate. The percentages of CR, CR+PR, and CR+PR+SD will be presented, as will the median duration of response. The lower bound of these percentages will be presented using the Clopper-Pearson Exact method to estimate the 95% confidence interval.

Additional analyses may also be performed as appropriate

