9.9.2.3 DURATION OF RESPONSE

Duration of response (DOR) defined as the interval from the first documentation of CR or PR to the

UTX-TGR-203

Dated: 20 December 2018 (Ver 2.0)

earlier of the first documentation of definitive disease progression or death from any cause. This variable will be summarized. Estimates of median DOR will be made using Kaplan-Meier methods.

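### Section 8.6.1 summarises duration of response with a raw mean and SD, which are not valid when some responders are still in response at the cut-off

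*Combined protocol and SAP*

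**What the plan says.** Section 8.6.1 defines DOR as running from a documented response to progression or death from any cause, and then states: "Duration of the response will be summarized using n (sample size), mean, standard deviation, median, minimum, and maximum for the responders". It mentions neither censoring nor Kaplan-Meier for DOR. The same section assigns Kaplan-Meier to PFS, which ends with the same events.

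Section 8.3 points forward to this text: "Overall response rate, CR, PR, SD, PFS and DOR will be calculated as detailed below".

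The statistical chapter treats DOR in four places:

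- Section 9.9.2.3: "This variable will be summarized. Estimates of median DOR will be made using Kaplan-Meier methods".
- Section 9.7 says which efficacy results will be presented, and for DOR adds only "as will the median duration of response", without naming an estimator.
- Section 9.2 gives the general default: "summary tabulations will display the number of observations, mean, standard deviation, median, minimum, maximum, and appropriate percentiles for continuous variables".
- The opening of Section 9 leaves to a later SAP "how censoring procedures will be applied to time to event related variables".

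DOR appears under the key secondary objectives in Section 2.1: "To assess the duration of response (DOR), Complete Response (CR) and progression-free survival (PFS".

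**The concern.** A raw mean or SD needs every duration to be complete. Here a responder's duration is complete only once progression or death has occurred. Any responder still in response at the cut-off contributes a lower limit, not a duration.

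There are two ways to compute a raw mean regardless, and both err in the same direction. Counting ongoing responses at their censored times replaces each unknown value with a smaller one. Leaving them out keeps mainly the short responses. A censoring rule in the later SAP would say where each ongoing response is cut off, but would not make either calculation valid.

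If the text is followed, the report would carry a DOR mean and SD driven more by length of follow-up than by durability of response. In a study without a control group, such figures may well be set beside those of other regimens with different follow-up.

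**Working it through.** The plan states no expected DOR, event count or precision for DOR, so there is no figure to reproduce. The check asks how far the raw statistics would fall short on the plan's own timeline.

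**Inputs from the documents**

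- Accrual, Section 4.4: "Enrollment is expected to be completed in approximately 12-16 months".
- Study duration about 36 months (Study Synopsis).
- First response scan at Cycle 3 Day 1 (Section 5, footnote 5). With 28-day cycles this is day 56, or 56/30.4375 = 1.84 months.

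**Assumptions**

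Exponential DOR with true median 12, 18, 24 or 36 months; response dated at the first scan; uniform accrual over 12 or 16 months; no drop-out; cut-off at 36 months, with 48 months as a sensitivity case because follow-up continues after Cycle 24.

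**Formulas**

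Follow-up after response, C, is uniform between a = cut-off − accrual − 1.84 and b = cut-off − 1.84. At 36 months, b = 34.16, and a = 22.16 (12-month accrual) or 18.16 (16-month accrual). With λ = ln 2 / median:

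- True mean = true SD = 1/λ.
- Censored share p = [exp(−λa) − exp(−λb)] / [λ(b − a)].
- Raw mean, ongoing responses counted at their censored times: (1 − p)/λ. Under an exponential DOR it is therefore too low by exactly the fraction p.
- Raw SD = √(E[X²] − mean²), where E[X²] = 2∫ t·exp(−λt)·P(C > t) dt.
- Mean of ended responses only = ∫ t·λ·exp(−λt)·P(C > t) dt / (1 − p).

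**Worked example** (median 24, accrual 12): λ = 0.02888; p = (0.5273 − 0.3729)/(0.02888 × 12) = 0.446; raw mean = (1 − 0.446) × 34.62 = 19.2 months, against a true mean of 34.6.

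**Results at 36 months** (12-month / 16-month accrual; durations in months)

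| True median | True mean = SD | Censored | Raw mean | Raw SD | Mean, ended only |
|---|---|---|---|---|---|
| 12 | 17.3 | 20% / 23% | 13.8 / 13.4 | 9.8 / 9.3 | 10.4 / 9.9 |
| 18 | 26.0 | 34% / 37% | 17.1 / 16.3 | 10.3 / 9.7 | 11.6 / 11.0 |
| 24 | 34.6 | 45% / 47% | 19.2 / 18.2 | 10.1 / 9.5 | 12.3 / 11.6 |
| 36 | 51.9 | 58% / 61% | 21.7 / 20.4 | 9.5 / 9.0 | 12.9 / 12.2 |

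Across the rows the raw mean is 20–61% too low, the raw SD 43–83% too low and the ended-only mean 40–77% too low. At 48 months the raw mean is 10–48% and the SD 27–74% too low.

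**Scan-dated check (simulation).** Progression was dated at the next protocol scan (Cycles 3, 6, 12, 18 and 24, then yearly) and ongoing responses were censored at the last scan. Against the same scan-dated durations without censoring, the mean is 32–68% and the SD 59–87% too low at 36 months; at 48 months the figures are 16–55% and 38–79%. In one corner (median 12, 48-month cut-off) late detection offsets the censoring: the scan-dated raw mean is 0–3% above the true mean of the underlying durations, while the SD is still 33–35% below.

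**The median.** With 40 assumed responders and a 36-month cut-off, a plain sample median would average 12.2, 17.3–18.0, 19.8–21.8 and 22.0–24.5 months for true medians of 12, 18, 24 and 36. It is therefore close at 12 to 18 and too low at 24 to 36. The Kaplan-Meier median would be not reached in 0%, 1%, 11–16% and 64% of simulated trials, which is the correct report in those cases.

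**The case against.** The strongest reply is that the valid method is already planned. Section 9.9.2.3 names the Kaplan-Meier median, Section 9.7 lists no mean or SD for DOR, and the SAP is still to come and may revise methods. On this view 8.6.1 is a leftover sentence in the measurement chapter, and the forward reference in 8.3 may mean only the definitions. It is also fair to say that the 9.2 default is for continuous variables in general and need not reach time-to-event variables.

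Much of this stands. The plan does have a sound DOR estimate, and no test, threshold or sample size uses the mean or SD. But 8.6.1 is the only place that lists DOR statistics explicitly, and nothing withdraws it. Section 9.9.2.3 says the variable will be summarised without saying how, and gives Kaplan-Meier to the median alone. A valid median does not validate the mean and SD beside it, and an SAP that dropped them would be departing from 8.6.1.

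A second objection concerns size. The true means above extend past the longest possible follow-up of 34.2 months, so no nonparametric method could estimate them here. Against the mean restricted to 34.2 months (14.9 months at a true median of 12; 25.0 at 36), the raw mean with ongoing responses counted is about 7–18% too low. The size therefore depends on the benchmark. The direction does not.

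**Conclusion.** The concern holds. As written, 8.6.1 calls for a raw mean and SD that are biased downward whenever responders remain in response at the cut-off, which is likely on a 36-month study with 12 to 16 months of accrual. Under the stated assumptions the raw mean is 20–61% below the full mean (about 7–18% below the restricted mean). More telling, the raw SD barely moves while the true SD triples. These sizes rest on an assumed exponential DOR, no drop-out and early response, none of which the documents supply.

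The consequence is limited to the reporting of a secondary endpoint. The overall response rate, PFS, the sample size and the planned Kaplan-Meier median are unaffected. It should be corrected, but it does not threaten the trial's main result. The unqualified median in 8.6.1 and 9.7 is a lesser matter: it can be read as the Kaplan-Meier median and only needs to say so.

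**What to change.** - **Section 8.6.1:** delete the mean and SD for DOR and refer to Section 9.9.2.3 for the Kaplan-Meier median. Report the number of responders, the number with progression or death and the number censored. If the minimum and maximum are kept, flag censored values, for example with a plus sign.
- **Section 9.9.2.3:** replace the unspecific statement that DOR will be summarised with these named statistics, so that the 9.2 default cannot be read as restoring the mean and SD.
- **Section 9.7:** state that the median DOR is the Kaplan-Meier median.

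If a mean is wanted, use a restricted mean to a pre-specified time. The DOR censoring rules still belong in the SAP, as Section 9 already foresees.

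The essential step is the deletion in 8.6.1 together with the named statistics in 9.9.2.3; the 9.7 wording and the plus sign are clarifications. The cost is wording in three sections, with no extra data, patients or time.
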